## 1) Evaluation in Period I

**Table 5.9-1 Analysis Visits in Period I**

Variables evaluated	Analysis visit
Platelets	Screening A, B, Day 1, Week 2 to 24 (every 2 weeks)
Treatment dose	Day 1, Week 2 to 24 (every 2 weeks)
QOL assessment (SF-36)	Day 1, Week 4, 12, 24
ITP Bleeding Score	Screening A, Day 1, Week 2 to 24 (every 2 weeks), LOV
ECOG Performance Status	Screening A, Day 1, Week 4 to 24 (every 4 weeks), LOV
Hematology (excluding platelets)	Screening A, B, Day 1, Week 2 to 24 (every 2 weeks), LOV
Serum chemistry	Screening A, Day 1, Week 2 to 24 (every 2 weeks), LOV
Urinalysis	Screening A, Day 1, Week 4 to 24 (every 4 weeks), LOV
Immunoglobulin test	Screening A, Day 1, Week 24, LOV
Vital signs	Screening A, B, Day 1, Week 2 to 24 (every 2 weeks), LOV
Plasma drug concentration	Pre-study drug administration: Week 2, 6; Post-study drug administration: Week 2 to 24 (every 2 weeks)

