3.2 Secondary Objectives

- 1) To evaluate the efficacy of R788 in patients with chronic ITP for the following points:
 - Maintenance of platelet count during long-term treatment with R788
 - Increase in platelet count during Period II for patients who received placebo in Period I
 - Improving of QOL
- 2) To investigate the safety of R788 in patients with chronic ITP
- 3) To investigate the pharmacokinetics of R788 in patients with chronic ITP (Period I).

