11.5 Period II (Early Transition Subjects)

11.5.1 ET Visit 1 (ET Day 1)

If the subject withdraws from Period I and transition to Period II, in principle, the study procedures on ET Day 1 will be performed on the same day as the last visit in Period I. When the study procedures on ET Day 1 are performed on the same day as the last visit for Period I, the procedures overlapping on ET Day 1 with the last visit of Period I may be omitted when the procedures on ET Day 1 are performed. If the procedures on ET Day 1 cannot be performed on the same day as the last visit of Period I, all procedures on ET Day 1 must be performed within 1 week from the last visit of Period I. All procedures on ET Day 1 should be performed on the same day.

- QOL evaluation (SF-36)^{a)}
- Study drug compliance
- ITP Bleeding Score
- Adverse events/concomitant medications
- ECOG Performance Status
- 12-lead ECG^{b)}

- Vital signs
- Laboratory tests (hematology, serum chemistry, and urinalysis)
- Immunoglobulin test
- Pregnancy test (women of childbearing potential only)
- Inclusion/exclusion criteria
- Enrollment for Transition to Period II
- Study drug dispensed (Period II)
- a) The QOL evaluation (SF-36) is performed prior to other procedures and assessments on ET Day 1.
- b) In principle, the 12-lead ECG is taken before vital signs, laboratory tests, immunoglobulin test, and pregnancy test (women of childbearing potential only).

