11.8 At Withdrawal

11.8.1 Withdrawal Visit

Subjects will undergo the Withdrawal Visit when they withdraw from Period I and do not transition to Period II, when they withdraw from Period III, or when they withdraw from Period III. Early transition subjects will not undergo the Withdrawal Visit. When the tests/examinations and evaluations on ET Day 1 do not meet "8.3.1 Transition criteria to Period II for subjects who withdraw from ," the tests/examinations and evaluations on ET Day 1 will be considered as those for Withdrawal Visit. Subjects who withdraw from the Non-dosing period will not undergo the Withdrawal Visit.

- QOL evaluation (SF-36)^{a)}
- Study drug compliance
- ITP Bleeding Score
- Adverse events/concomitant medications
- ECOG Performance Status
- 12-lead ECG^{b)}
- Vital signs
- Laboratory tests (hematology, serum chemistry, and urinalysis)
- Immunoglobulin test^{c)}
- Pregnancy test (women of childbearing potential only)
- Pharmacokinetics^{d)}
- a) The QOL evaluation should be performed only for subjects who withdraw from Period I and do not transition to Period II or subjects who withdraw from Period II. If the QOL evaluation is performed, it should be performed before the other tests/examinations and evaluations.
- b) The 12-lead ECG should be performed only for subjects who withdraw from Period I and do not transition to Period II or subjects who withdraw from Period II. In principle, the 12-lead ECG is taken before vital signs, laboratory tests, immunoglobulin test, immunological test, pregnancy test (women of childbearing potential only), and pharmacokinetics.
- c) The Immunoglobulin test should be performed only for subjects who withdraw from Period I and do not transition to Period II or subjects who withdraw from Period II.
- d) Pharmacokinetics should be examined only for subjects who withdraw from Period I and do not transition to Period II. The

time of the last study drug administration before blood sampling to the date of blood sampling are not specified.

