## 5.9 Analysis Visits

Unless otherwise specified, each analysis variable will be evaluated at the following time points.

- Data obtained outside the time window of analysis visits and data from unscheduled visits

will be excluded from summarization at each time point.

- For analyses of each treatment period, test data obtained outside the range of “the day of the last dose plus the specified number of days” will be excluded from the analysis. The specified number of days is 3 days for Period I and 7 days for Periods II and III.
- The last observed visit (LOV) other than the non-dosing period is defined as the last scheduled visit or the discontinuation visit, whichever is later, performed within the range of “the day of the last dose plus the specified number of days” for each period. The specified number of days is 3 days for Period I and 7 days for Periods II and III.
- The LOV in the non-dosing period is defined as the data for the latest test among all tests performed up to the last day of the non-dosing period.
- For all variables, Day 1 of Period I will be used as a baseline and only changes at time points after Day 1 of each period will be evaluated.
- In the non-dosing period, change from the start of the non-dosing period will be evaluated in addition to the change from Period I Day 1. Time points after Day 1 of the non-dosing period will be evaluated.

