**Table 5.9-2 Time Windows for Each Analysis Visit in Period I**

Analysis visit	Target study day a)	Lower limit	Upper limit
Screening A	-28	-31	-25
Screening B	-14	-17	-11
Day 1	1	1	1
Week 2 to 24	$7 \times x + 1^b)$	Target study day -3	Target study day +3

a) The first day of study drug administration in Period I is defined as Day 1, and the day before the first day of study drug administration as Day -1.

b) x: Number of weeks

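### SF-36 answers given on leaving Period I between the Week 12 and Week 24 windows enter no Period I summary by randomised arm, so the descriptive Week 24 row covers only subjects still in the period

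*SAP*

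**What the plan says.** Quality of life is a secondary objective (Protocol 3.2: "Improving of QOL"), and Period I is the only placebo-controlled part of the study.

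**Collection.** Besides the scheduled visits, SF-36 is completed at exit.
- Protocol 11.8.1, Withdrawal Visit: "The QOL evaluation should be performed only for subjects who withdraw from Period I and do not transition to Period II", or who withdraw from Period II.
- Protocol 11.5.1, early transition: "The QOL evaluation (SF-36) is performed prior to other procedures and assessments on ET Day 1". Protocol 11.8.1 adds that early-transition subjects have no Withdrawal Visit.

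**Analysis.**
- SAP Table 5.9-1 lists SF-36 at "Day 1, Week 4, 12, 24". The bleeding score, ECOG, laboratory, immunoglobulin and vital-sign rows of that table also have a last observed visit (LOV), which "is defined as the last scheduled visit or the discontinuation visit, whichever is later". SF-36 and platelets have none.
- SAP Table 5.9-2 sets the lower window limit at "Target study day -3" and the upper limit three days after target.
- SAP 5.9 leaves out of the by-visit summaries: "Data obtained outside the time window of analysis visits and data from unscheduled visits".
- SAP 6.2 provides no imputation for SF-36.
- SAP 5.9 (Evaluation in Period II) and Table 5.9-7 use ET Day 1 data as Week 24 of the Period II evaluation. SAP 5.9 also states that "only changes at time points after Day 1 of each period will be evaluated".
- SAP 11.2.1.7 plans summary statistics only.

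**The concern.** Under Protocol 8.3.1, transition for lack of efficacy opens after Week 12, and the Period I schedule marks Weeks 12 to 22 as visits at which it can happen. That is almost exactly the stretch with no SF-36 analysis visit. Leaving for lack of efficacy depends on the platelet count, and SAP 11.1 classes anyone who leaves for an adverse event or lack of efficacy as a non-responder. The Week 24 SF-36 row is therefore a summary of stayers. The R788 arm is expected to contain more responders, so losing non-responders shifts its mix by more percentage points than it shifts the placebo mix. If responders feel better than non-responders, a reader comparing the arms at Week 24 would see a somewhat flattering contrast, although the leavers' answers had been collected.

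**Working it through.** **1. The plan's own figure.** No design figure is given for SF-36. The only one is the 89% in Protocol 8.9.2, the chance that the observed response rate is higher on R788 than on placebo. With X ~ Bin(16, 0.178) and Y ~ Bin(8, 0.020), summing the joint probabilities where X/16 > Y/8 gives 89.3%, so it reproduces. It does not bear on this point, but its inputs are used below.

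**2. Which days are covered.** The target is Day 7x + 1, plus or minus 3.
- Week 4: Days 26 to 32
- Week 12: Days 82 to 88
- Week 24: Days 166 to 172

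An exit SF-36 on Days 89 to 165 falls in no Period I window.

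**3. Where that answer goes.**
- *Withdrawal Visit:* no analysis visit of its own, no LOV and no imputation, so it is in no by-visit summary.
- *ET Day 1:* tabulated as Period II Week 24. Under SAP section 3, the R788-R788 group there holds only R788 subjects who left Period I early. The P-R788 group holds placebo completers and placebo early leavers together. The R788 completers are not in that table, so it cannot restore the randomised comparison.
- *Exit at the Week 12 visit:* counts at Week 12, but not at Week 24.

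**4. Possible change in the Week 24 mix.** Inputs from Protocol 8.9: 16 and 8 subjects; responder rates 17.8% and 2.0%. Assumed, because the documents give no exit rate: a share w of non-responders leaves before the Week 24 window, equal in both arms, and every responder stays.

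- R788 remaining = 16 × (1 − 0.822w), of whom 16 × 0.178 = 2.85 are responders.
- Placebo remaining = 8 × (1 − 0.98w), of whom 8 × 0.020 = 0.16 are responders.

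| w | n R788 / placebo | Responder share | Gap (points) | Gap ÷ 15.8 |
|---|---|---|---|---|
| 0 | 16 / 8 | 17.8% / 2.0% | 15.8 | 1.00 |
| 0.25 | 12.7 / 6.0 | 22.4% / 2.6% | 19.8 | 1.25 |
| 0.50 | 9.4 / 4.1 | 30.2% / 3.9% | 26.3 | 1.66 |
| 0.75 | 6.1 / 2.1 | 46.4% / 7.5% | 38.9 | 2.46 |

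At w = 0.75 the chance that no placebo subject has a Week 24 SF-36 is (0.98 × 0.75)^8 = 8.5%.

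**5. What that could mean for SF-36.** Suppose responders score D higher than non-responders and nothing else matters. The arm difference then grows by D times the increase in the gap. Taking D = 1 between-subject SD for illustration (the documents give no value), the increase is 0.04, 0.11 and 0.23 SD for the three values of w. The standard error, √(1/n_R + 1/n_P), is 0.49, 0.59 and 0.80 SD. The shift is therefore about 8%, 18% and 29% of one standard error, and half that if D = 0.5 SD.

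**The case against.** Much can be said for the plan.

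- **A reader might infer that exit SF-36 is thrown away.** For early-transition subjects it is not. ET Day 1 values are tabulated in the Period II evaluation by original arm. Only the off-window Withdrawal Visit answer goes unused in the by-visit summaries.
- **A reader might infer that the SF-36 treatment difference will be 1.25 to 2.5 times too large.** The documents do not support that. Those ratios describe the responder mix under assumed exit rates. Exit for lack of efficacy requires the investigator to judge the risk of continuing unacceptable (Protocol 5.3.1), so w cannot be predicted. No SF-36 arm difference or test is planned, and SAP 6.5 treats everything but the primary endpoint as reference only. There is no type I error issue.
- **A reader might take Week 24 as the plan's single quality-of-life result.** The plan does not say so. Weeks 4 and 12 are summarised by arm as well and are largely unaffected.
- **Numbers are visible.** SAP section 4 includes the number of subjects in the summary statistics, and SAP 8.2 tabulates discontinuations by reason.
- **The LOV pattern is coherent.** In Period I it is given to safety variables, while both efficacy variables use fixed visits. The SF-36 LOV in the non-dosing period is a later addition for a period with few scheduled visits (SAP 16.3). Its absence in Period I is not in itself an inconsistency.

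All of this stands and limits the weight of the point. It does not fill the gap: no planned table sets the exit SF-36 of leavers beside the Week 24 SF-36 of stayers within each randomised arm.

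**Conclusion.** The gap is real and follows from the SAP tables. An SF-36 taken on leaving Period I on Days 89 to 165 is in no Period I summary by randomised arm, and the descriptive Week 24 row covers only subjects still in the period. The direction of the change in mix follows from SAP 11.1 for exits due to adverse events or lack of efficacy. For adverse-event leavers the non-responder label is partly a matter of definition, so its link to quality of life is weaker.

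The size is not known from the documents. The rise from 15.8 points to about 20, 26 and 39 rests on equal exit in both arms at 25%, 50% or 75% of non-responders and on all responders staying. The effect on SF-36 also needs a quality-of-life gain in responders that the documents do not state, and it may be small relative to the standard error. This is an inexpensive improvement to a secondary descriptive analysis. It does not affect the primary result.

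**What to change.** Add to the SF-36 row of SAP Table 5.9-1, and to SAP 11.2.1.7, a supplementary end-of-Period-I value. Define it as the Week 24 assessment or, if there is none, the Withdrawal Visit or ET Day 1 assessment. Present it with change from Period I Day 1 by randomised arm.

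Two details need wording:
- Name ET Day 1 explicitly. Early-transition subjects have no Withdrawal Visit, so the existing LOV definition may not pick up their answer.
- State how the rule in SAP 5.9 that drops Period I data later than three days after the last dose applies to ET Day 1. Protocol 11.5.1 allows that assessment up to one week after the last Period I visit, so the rule could exclude some of these subjects.

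Keep the Week 24 row. The number contributing there is already part of the planned summary statistics and needs no change.

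The cost is one table entry, one sentence of definition and one output row; no new data are needed. The downside is that the values come from different weeks, so the row supplements Week 24 and does not replace it.

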**Table 5.9-2 Time Windows for Each Analysis Visit in Period I**

Analysis visit	Target study day a)	Lower limit	Upper limit
Screening A	-28	-31	-25
Screening B	-14	-17	-11
Day 1	1	1	1
Week 2 to 24	$7 \times x + 1^b)$	Target study day -3	Target study day +3

a) The first day of study drug administration in Period I is defined as Day 1, and the day before the first day of study drug administration as Day -1.

b) x: Number of weeks

## 2) Evaluation during long-term treatment of R788

**CONFIDENTIAL**

Kissei Pharmaceutical Co., Ltd.

Protocol No.: R788-1301

Statistical Analysis Plan

Version: 3.0

**Table 5.9-3** Analysis visits during long-term treatment of R788

Variables evaluated	Analysis visit
Platelets	Screening A, B, Day 1, Week 2 to 24 (every 2 weeks), Week 28 to 52 (every 4 weeks)
Treatment dose	Day 1, Week 2 to 24 (every 2 weeks), Week 28 to 52 (every 4 weeks)
QOL assessment (SF-36)	Day 1, Week 4, 12, 24, 52
ITP Bleeding Score	Screening A, Day 1, Week 2 to 24 (every 2 weeks), Week 28 to 52 (every 4 weeks), LOV
ECOG Performance Status	Screening A, Day 1, Week 4 to 52 (every 4 weeks), LOV
Hematology (excluding platelets)	Screening A, B, Day 1, Week 2 to 24 (every 2 weeks), Week 28 to 52 (every 4 weeks), LOV
Serum chemistry	Screening A, Day 1, Week 2 to 24 (every 2 weeks), Week 28 to 52 (every 4 weeks), LOV
Urinalysis	Screening A, Day 1, Week 4 to 24 (every 4 weeks), Week 28 to 52 (every 12 weeks), LOV
Immunoglobulin test	Screening A, Day 1, Week 24, Week 52, LOV
Vital signs	Screening A, B, Day 1, Week 2 to 24 (every 2 weeks), Week 28 to 52 (every 4 weeks), LOV

**Table 5.9-4** Time Windows for Each Analysis Visit during Long-term Treatment of R788

Analysis visit	Target study day a)	Lower limit	Upper limit
Screening A	-28	-31	-25
Screening B	-14	-17	-11
Day 1	1	1	1
Week 2 to 24	$7 \times x + 1^b)$	Target study day -3	Target study day +3
Week 28 to 52	$7 \times x + 1^b)$	Target study day -7	Target study day +7

a) The first day of study drug administration in Period I is defined as Day 1, and the day before the first day of study drug administration as Day -1.

b) x: Number of weeks

### 3) Evaluation in Period II

The following data will be used as Week 24 to 52 data:

- Data from Week 24 to 52 of subjects who received placebo in Period I, completed Period I, and transitioned to Period II.
- Data from early transition Day 1 to early transition Week 28 of subjects who discontinued Period I and early transitioned to Period II.

**Table 5.9-5** Analysis Visits in Period II

Variables evaluated	Analysis visit
Platelets	Week 24 to 52 (every 4 weeks)
Treatment dose	Week 24 to 52 (every 4 weeks)
QOL assessment (SF-36)	Week 24, Week 52
ITP Bleeding Score	Week 24 to 52 (every 4 weeks), LOV
ECOG Performance Status	Week 24 to 52 (every 4 weeks), LOV
Hematology (excluding platelets)	Week 24 to 52 (every 4 weeks), LOV
Serum chemistry	Week 24 to 52 (every 4 weeks), LOV
Urinalysis	Week 24, Week 28 to 52 (every 12 weeks), LOV
Immunoglobulin test	Week 24, Week 52, LOV
Vital signs	Week 24 to 52 (every 4 weeks), LOV

**CONFIDENTIAL**

Kissei Pharmaceutical Co., Ltd.

Protocol No.: R788-1301

Statistical Analysis Plan

Version: 3.0

**Table 5.9-6** Time Windows for Each Analysis Visit in Period II (for those who completed Period I)

Analysis visit	Target study day a)	Lower limit	Upper limit
Week 24 to 52 (every 4 weeks)	$7 \times x + 1^b)$	Target study day -7	Target study day +7

a) The first day of study drug administration in Period I is defined as Day 1, and the day before the first day of study drug administration as Day -1.

b) x: Number of weeks

**Table 5.9-7**

Time Windows for Each Analysis Visit in Period II (for those who early transitioned)

Analysis visit	Target study day a)	Lower limit	Upper limit
Week 24	1	-1	1
Week 28 to 52 (every 4 weeks)	$7 \times (x-24) + 1^b)$	Target study day -7	Target study day +7

a) The first day of study drug administration in Period II is defined as Day 1 and the day before the first day of study drug administration as Day -1.

b) x: Number of weeks

#### 4) Evaluation in non-dosing period

Day 1 of the non-dosing period is defined as Week 52 of Period II for subjects who completed Period I, and as early transition Week 28 for subjects who early transitioned to Period II. Day 1 of Period III is defined as Week 4 of the non-dosing period.

**Table 5.9-8**

Analysis Visits in Non-Dosing Period

Variables evaluated	Analysis visit
Platelets	Day 1, Week 2, Week 4, LOV
ITP Bleeding Score	Day 1, Week 2, Week 4, LOV
QOL assessment (SF-36)	Day 1, Week 2, Week 4, LOV
ITP Bleeding Score	Day 1, Week 2, Week 4, LOV
ECOG Performance Status	Day 1, Week 2, Week 4, LOV
Hematology (excluding platelets)	Day 1, Week 2, Week 4, LOV
Serum chemistry	Day 1, Week 2, Week 4, LOV
Urinalysis	Day 1, Week 2, Week 4, LOV
Immunoglobulin test	Day 1, Week 2, Week 4, LOV
Vital signs	Day 1, Week 2, Week 4, LOV

**Table 5.9-9**

Time Windows for Each Analysis Visit in Non-Dosing Period

Analysis visit	Target study day a)	Lower limit	Upper limit
Day 1	1	1	1
Week 2, Week 4	$7 \times x + 1^b)$	Target study day -3	Target study day +3

a) Day 1 is defined as the day of Week 52 visit for subjects who completed Period I and the day of Week 28 visit for those who early transitioned to Period II.

b) x: Number of weeks

#### 5) Evaluation in Period III

Day 1 is the first visit in Period III.

**Table 5.9-10 Analysis Visits in Period III**

Variables evaluated	Analysis visit
Platelets	Day 1, Week 8 (every 8 weeks thereafter)
Treatment dose	Week 8 (every 8 weeks thereafter)
ITP Bleeding Score	Day 1, Week 8 (every 8 weeks thereafter)
ECOG Performance Status	Day 1, Week 8 (every 8 weeks thereafter)
Hematology (excluding platelets)	Day 1, Week 8 (every 8 weeks thereafter)
Serum chemistry	Day 1, Week 8 (every 8 weeks thereafter)
Urinalysis	Day 1, Week 8 (every 8 weeks thereafter)
Vital signs	Day 1, Week 8 (every 8 weeks thereafter)

**Table 5.9-11 Time Windows for Each Analysis Visit in Period III**

Analysis visit	Target study day a)	Lower limit	Upper limit
Day 1	1	1	1
Week 8 (every 8 weeks thereafter)	$7 \times x + 1^b)$	Target study day -14	Target study day +14

a) The first visit in Period III is defined as Day 1, and the day before the first visit as Day -1.

b) x: Number of weeks

## 6) Evaluation in R788 treatment period

Day 1 of the R788 treatment period is defined as the first day of study drug administration in Period I for subjects who received R788 in Period I, and as the first day of study drug administration in Period II for those who received placebo in Period I and transitioned to Period II. No analysis visit-specific analysis will be performed for evaluation in the R788 treatment period.

## 7) Evaluation in the entire study period

Day 1 is defined as the first day of study drug administration in Period I. No analysis visit-specific analysis will be performed for evaluation in the entire study period.

# 6. Statistical/Analytical Issues

## 6.1 Adjustments for Covariates

Analyses adjusted for covariates will not be performed.

## 6.2 Handling of Dropouts and Missing Data

When data to be used for analysis are missing, they will be handled as missing, and no statistical imputation will be performed, excluding the variables listed in “[5 Data Handling](#)” and below. Last observation carried forward (LOCF) imputation will be applied to the primary endpoint. For details, see “[11.1 Primary Endpoint](#).”

## 6.3 Interim Analyses and Data Monitoring

### 6.3.1 Timing of analysis

#### 1) First data cutoff

After all subjects have completed Period I, the following data collected by the first data cut-off date will be analyzed for Period I, long-term treatment of R788, R788 treatment period, and the

- Period I data of all subjects
- Period II data of subjects who completed Period II
- Follow-up data of subjects who completed the follow-up period

2) Second data cutoff

After all subjects have completed the non-dosing period, all data collected by the second data cut-off date will be analyzed for Period I, long-term treatment of R788, Period II, non-dosing period, Period III, R788 treatment period, and the entire study period.

## **6.4 Multicenter Studies**

No site-specific analysis will be performed because the per site sample size is not large enough.

## **6.5 Multiple Comparison/Multiplicity**

### **6.5.1 Multiplicity for multiple analyses and multiple analysis visits**

The primary endpoint is defined as stable platelet response based on platelet counts from Week 14 to Week 24 in Period I, and other variables, and time points will be used for reference only. Therefore, multiplicity adjustment for multiple analysis visits will not be performed.

